2.0 STUDY DESIGN

We will recruit 170 community-dwelling PLWH (20 for focus groups, 150 for the RCT) using the services of the UCSD HIV Neurobehavioral Research Program (HNRP) and the associated NIMH-funded HIV Neurobehavioral Research Center (HNRC) (P30 MH062512) and the Translational Methamphetamine AIDS Research Center (TMARC) (P50 DA026306). These centers have supported numerous multidisciplinary endeavors among PLWH over the past 20+ years and facilitate PLWH recruitment from the San Diego area and comprehensive neuromedical testing. While we will include participants who have previously engaged in research studies at the HNRP, we will also use our community outreach facilities to recruit PLWH who have not previously participated in research; this approach will enable a more appropriate representation of the general population and maximize the number of available participants. Recruitment and testing will be facilitated by an extensive research team.

3.0 SELECTION AND ENROLLMENT OF PARTICIPANTS

3.1 Inclusion Criteria

- 3.1.1. Ability of participant to provide informed consent.
- 3.1.2. Age 18 or older.
- 3.1.3. HIV infection documented at the University of California, San Diego (UCSD) HIV Neurobehavioral Research Program (HNRP) or assessed by an HIV test at screening

- 3.1.4 proficient in English
- 3.1.5 Physically capable of participating in moderate PA as screened by the Physical Activity Readiness Questionnaire
- 3.1.6 Consent from primary care physician to participate in the study
- 3.1.7 Able to consume walnuts - no nut allergies

3.2 Exclusion Criteria

- 3.2.1. Any physical conditions that would prevent moderate physical activity or where moderate physical activity would represent a health risk for the individual, including a history of myocardial infarction or stroke
- 3.2.2 Unwillingness or inability to participate in daily text messaging
- 3.2.4. Tree nut allergy that would prevent walnut consumption or other food restrictions that would prevent participation in the Mediterranean-style diet intervention (e.g., unable to eat fish or use olive oil for cooking).

4.0 CLINICAL MANAGEMENT ISSUES

4.1 Adverse Events

We have taken great care to minimize the risks associated with text messaging in this study, including eliminating any information in the SMS content that could identify the HIV status of the participants. For example, we will not use any medication names in messages (e.g., identifying an HIV medication) or include content that could be used by a third party to identify a particular medical condition, but will utilize generic messages that ask about relevant physical conditions and limitations (e.g., do you have muscle aches today?). We will not include any personally identifiable information such as the name of the participant in the SMS content sent to each subject or stored on mobile phones provided to participants. Text messages will include geographical landmarks such as nearby locations to engage in PA or the names of specific grocery stores to purchase food items; there is a risk this information could be accessed by an unauthorized person if the cell phone is lost or stolen.

Participants may experience anxiety or embarrassment related to one's personal PA or diet behavior (e.g., a lack of physical activity) or feelings of inadequacy with limited progress during the intervention. Participants in the focus groups may experience nervousness from participating in a group process activity or speaking in front of others regarding the issues that may affect PA or diet. Participants will be motivated to engage in moderate PA, including walking, and light PA to reduce and interrupt SB. No vigorous PA will be required. Some participants may experience mild muscle fatigue or soreness. Standard clinical interview procedures, including administration of PA and diet questionnaires, pose little risk to

participants. The blood draw procedure includes the risk of minor discomfort, bruising, fainting, or dizziness.

As with any HIV study, one potential risk is that of breach of confidentiality wherein a person's HIV status, sexual behaviors, or other sensitive information might be disclosed, resulting in embarrassment or prejudicial treatment by others. We will adhere to the standard risk management protocol in this regard, including use of participant identification numbers, locked data cabinets, and password protected computer databases. To ensure confidentiality, only the participant's code number will appear on all data forms as is standard at the HNRP. All paper-based records, forms, and data are kept in a locked interior file room. All medical records and demographic data also are locked in file cabinets within the file room. Computer records are protected by standard measures that limit access to the data to selected research project personnel. The electronic data are protected by multiple levels of password access, including to individual machines, the server, and to the central database. An HNRP Confidentiality Committee performs regular inspections to monitor procedures. In addition, the HNRP is protected from subpoena of confidential records by a Federal Certificate of Confidentiality.

4.2 Clearance from Primary Care Physician

Participants will be excluded for any physical conditions that would prevent moderate PA or where moderate PA would represent a health risk for the individual, including a history of myocardial infarction or stroke, pain in the chest when exercising, chronic joint problems aggravated by exercise, or a history of falls or balance problems. To minimize the probability of adverse events, participants will be screened for medical conditions using the Physical Activity Readiness Questionnaire; any indication of physical conditions that preclude moderate PA will result in the exclusion of the participant from the study. As an additional safeguard, each participant's PCP will be contacted, with participant consent, to verify if there are any medical issues that would prevent involvement in this study. Study personnel will initially contact the physician by phone, after receiving written consent from the participant, to determine if the PCP is willing to provide medical clearance for the intervention. If the participant's doctor agrees to do so, we will mail the PCP a medical clearance form that describes the SMS study and lists the options for moderate PA, such as walking, household activities (e.g., gardening). The form will provide the physician with the option to endorse study participation, deny participation due to known risks, postpone clearance contingent on further medical assessment, or acknowledge that they lacked adequate knowledge of the patient's medical history to make an informed decision. The form will also allow the PCP to indicate that some activities, but not others are appropriate for the patient (e.g., walking is acceptable, but not climbing stairs). If the participant is enrolled, this information will be incorporated into the SMS prompts they receive. We will request that the PCP mail the completed form back to the PI. Participants will not be permitted to start the intervention until this written medical clearance is received. If the participant reports an adverse event or contraindication to moderate PA during the intervention (e.g., muscle soreness, shortness of breath), he or she will be suspended from the study until written medical clearance is again provided by the PCP. This will involve a second medical clearance form that will describe the adverse event and allow the PCP to indicate if the individual can resume the program, should discontinue, or if more evaluation is needed.

Ongoing medical treatment for HIV will not be altered or modified in any way for research

purposes. All subjects will be provided with PA safety and injury prevention recommendations before beginning the study, including instructions on warming up and stretching activities. Participants will be counseled that it is appropriate to gradually increase their PA (e.g., increase step counts by 10% per week) to reduce the risk of musculoskeletal injury and adverse events. During the initial enrollment and screening process, participants will be asked to phone the PI if any adverse events occur during study participation. In an emergency situation where participants are in need of immediate help as a result of an adverse event, the participants will be informed that they should first call 911 and then report the incident to the study staff as early as possible. Participants will also be contacted by telephone on a monthly basis by the PI to inquire about any adverse events, including chest pain, dizziness, or falls. Subjects will also receive regular text messages that will solicit information about any adverse events associated with their PA and any affirmative responses will be received by the PI who will contact the participant. In the case of any adverse events, participant PA activities will be immediately discontinued and the subject's PCP will be contacted to coordinate appropriate evaluation and treatment. Participant text logs will be monitored on a daily basis to ensure that no serious problems have occurred and to supervise each individual's continuing participation in the study. Participants are informed that they may withdraw from the research at any time if they find any aspect objectionable.

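### Section 4.2 describes the consequence of an adverse event in two unreconciled ways and does not say whether outcome follow-up continues, so week-24 or week-48 data could be lost for an intervention-related reason

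*Combined protocol and SAP*

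**What the plan says.** Section 4.2 (Clearance from Primary Care Physician) deals with adverse events in two places.

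- The first applies when a participant "reports an adverse event or contraindication to moderate PA during the intervention (e.g., muscle soreness, shortness of breath") and states that "he or she will be suspended from the study until written medical clearance is again provided by the PCP". A second clearance form is then used to "allow the PCP to indicate if the individual can resume the program, should discontinue, or if more evaluation is needed". No time limit is given.
- The second, later in the section, reads: "In the case of any adverse events, participant PA activities will be immediately discontinued and the subject's PCP will be contacted". It mentions neither suspension from the study nor a second clearance.

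Section 4.1, describing the activity that participants will be encouraged to do, says: "Some participants may experience mild muscle fatigue or soreness".

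Events are actively sought. Section 4.2 provides for text messages ("Subjects will also receive regular text messages that will solicit information about any adverse events associated with their PA") and for calls ("Participants will also be contacted by telephone on a monthly basis by the PI to inquire about any adverse events").

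Section 5.1 plans three mixed-model analyses: all available data under missing-at-random, baseline observation carried forward (BOCF), and completers only. It does not say how a suspended participant is classified. Section 5.2 assumes 20% dropout, leaving 40 in each arm, and does not mention suspension.

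**The concern.** The two statements differ in scope (the study as a whole, or PA only) and in trigger (an event or contraindication during the intervention, or any adverse event). Neither sets a severity threshold, and soreness is both a foreseen effect of the activity and a named trigger. Site staff could therefore reasonably handle the same event in different ways, and one way might end outcome collection.

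What is at stake is missing outcome data whose cause is related to the intervention. The daily activity prompts are described for the intervention, so such losses would plausibly be more frequent in the two iSTEP arms than in control. A participant removed because activity caused symptoms may also have changed less than one who stayed. The missing-at-random assumption would then be doubtful, and the three analyses in section 5.1 could diverge because of an administrative rule. Outcomes not collected at week 24 or week 48 cannot be recovered at analysis.

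**Working it through.** **1. The texts side by side**

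| | First statement in 4.2 | Second statement in 4.2 |
|---|---|---|
| Trigger | Adverse event or contraindication to moderate PA during the intervention; soreness is an example | Any adverse event |
| Consequence | Suspension from the study | PA stopped, PCP contacted |
| How it ends | PCP form: resume, discontinue, or evaluate further | Not stated |
| Week-24 and week-48 visits | Not stated | Not stated |

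The two can be combined into one sequence: stop PA, contact the PCP, wait for the form. The text does not say that this is intended.

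**2. The plan's own figure**

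Section 5.2: 50 × (1 − 0.20) = 40 per arm, which reproduces. For 40 v 40, two-sided alpha 0.05 and 80% power, a two-sample t-test on change detects d = 0.634. The normal approximation gives (1.960 + 0.842) × √(1/40 + 1/40) = 0.626. This agrees with the medium to large effect that section 5.2 claims for two-visit outcomes. No stated figure is wrong.

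**3. Illustration of lost power**

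Assumption, not in the documents: suspension permanently removes a further 10%, 20% or 30% of the 40 completers in one active arm, on top of the 20% dropout, and control stays at 40. Power is from the noncentral t with noncentrality d / √(1/40 + 1/n).

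| Extra loss | n active | Noncentrality at d = 0.634 | Power at d = 0.634 | Power at d = 0.8 |
|---|---|---|---|---|
| 0% | 40 | 2.84 | 80% | 94% |
| 10% | 36 | 2.76 | 78% | 93% |
| 20% | 32 | 2.67 | 75% | 91% |
| 30% | 28 | 2.57 | 72% | 89% |

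The d = 0.8 column takes the conventional value for a large effect, which is what section 5.2 claims for three-visit outcomes. Its figures are not available, so 0.8 is also an assumption.

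**4. Illustration of bias, by analysis**

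- *Completers only.* If a fraction f of would-be completers is removed and they would have changed δ SD less than the rest, the active-arm mean change is overstated by f × δ. With f from 0.10 to 0.30 and δ from 0.3 to 0.5 (both assumed), this runs from 0.10 × 0.3 = 0.03 SD to 0.30 × 0.5 = 0.15 SD.
- *BOCF.* Each missing participant is given zero change. If control does not change, the estimate is the completers' mean change multiplied by the fraction of the active arm observed: 40/50 = 0.80 with no extra loss, then 36/50 = 0.72, 32/50 = 0.64 and 28/50 = 0.56. The pull is generally towards no effect.
- *All available data.* The model keeps the visits that were made, but is valid only if the missing values are missing at random given the observed data. Loss prompted by activity-related symptoms is a reason to doubt that.

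**5. Which contrasts are exposed**

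The iSTEP v control contrasts are the most exposed. Both active arms receive the PA and sedentary-behaviour component, so similar suspension in each would largely cancel as bias in the combined v PA-alone contrast.

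**The case against.** The strongest reply is that this is a loose sentence and not a defect. Suspension is triggered during the intervention, the section concerns medical clearance for the intervention, and the next sentence speaks of resuming the programme. The natural meaning may be a pause in activity prompting. No text cancels an assessment. Visit outcomes fall only at baseline, 24 and 48 weeks, so a pause that ends before a visit costs none of them. The daily step data most exposed to a pause serve an exploratory analysis.

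This stands in part. It rules out two stronger readings that a reader might infer. One is that section 4.2 contradicts itself outright; the statements can be read as successive steps. The other is that outcome data will be lost mainly in the active arms, biasing every hypothesis. The documents do not support that: the monthly call is not restricted by arm, control-arm messaging is not described, and the combined v PA-alone contrast is much less exposed.

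The sizes are also open to challenge. They treat a temporary suspension as permanent, and they add it to a 20% dropout that may already cover some of it. The value d = 0.634 is back-calculated so that power starts at exactly 80%. At d = 0.8, power stays at 89% for 40 v 28, and at 84% even if both compared arms fall to 28.

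What the reply does not remove is the gap itself. The words used are suspension from the study, the PCP can answer that the participant should discontinue, there is no time limit, and no sentence keeps such a participant in follow-up.

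**Conclusion.** The point holds as an unreconciled ambiguity with a possible consequence for outcome data. It does not hold as a demonstrated loss or bias. If suspension from the study is applied literally, or the PCP advises discontinuation, week-24 or week-48 outcomes could be missing for an intervention-related reason, plausibly more often in the PA arms than in control.

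The size cannot be derived from the documents. Under the assumed permanent extra loss of 10% to 30% of completers in one active arm, the power cost at d = 0.634 is 2 to 8 percentage points. Overstatement of 0.03 to 0.15 SD applies only to a completers-type analysis, while BOCF would tend to err the other way. If suspensions are short, the effect on visit outcomes may be nil. The change is still worth making before enrolment, because it is cheap and the data at risk cannot be collected afterwards.

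**What to change.** 1. Reconcile the two statements in section 4.2 so that one procedure is described. Which clinical rule applies is for the investigators.
2. State in sections 4.2 and 5.1 that suspending or stopping the intervention is not withdrawal from follow-up. Suspended participants are still invited to the planned week-24 and week-48 assessments where safe, and are analysed in their randomised arm.
3. In section 5.1, say how suspended participants count in each of the three analyses, including whether they are completers.
4. Record the start and end dates of each suspension and report them by arm, so that any imbalance is visible.

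The cost is protocol wording and a small record for each suspension. The downside is that staff must keep scheduling already-planned visits for suspended participants.

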People who live with HIV (PLWH) experience a high incidence of neurocognitive deficits and HIV-associated non-AIDS (HANA) disorders, including cardiovascular disease (CVD), metabolic dysfunction, and autonomic decline. While antiretroviral treatment (ART) has reduced AIDS-related morbidity, both the virus and the medications are associated with lipid disorders that also increase CVD risk, including dyslipidemia and lipodystrophy. Consequently, the development of effective lifestyle interventions to reduce the incidence of HIV-associated neurocognitive disorders (HAND) and decrease metabolic disorders is a high priority. Physical activity (PA) has been utilized as an effective tool to improve health in PLWH, but may not be sufficient by itself to improve lipid levels. Existing PA interventions in PLWH typically required strenuous PA and significant resources that limit feasibility for many people living with the disease. Recent work indicates that interrupting periods of sedentary behavior (SB), independent of PA, also has a significant beneficial effect on metabolic function, but SB has not been well-studied in PWLH. Mediterranean-style diets (MedDiet) are also effective at improving CVD risk factors in HIV-uninfected individuals and are reported to reduce cognitive decline in persons at risk for Alzheimer's disease, but have not been widely tested in PWLH. We recently developed a novel and personalized Short Message Service (SMS) mobile phone text messaging intervention (iSTEP) that is designed to increase moderate PA in PLWH. Our objective is to expand upon this work and conduct an RCT examining the efficacy of iSTEP in combination with a mobile mHealth MedDiet intervention tailored to PLWH. 150 PLWH will be randomly assigned to a control group ($n = 50$), a 6-month iSTEP group with just a PA/SB intervention ($n = 50$), or a 6-month intervention with both PA/SB and MedDiet components ($n = 50$), where participants receive daily interactive SMS/MMS messages designed to increase moderate PA, reduce SB, and promote adherence to a MedDiet, including walnut consumption. PA/SB will be quantified by accelerometer, Fitbit step counts, and self-report, while MedDiet adherence will be assessed by self-report (Diet History Questionnaire and weekly SMS feedback) and also objective measures (polyunsaturated fatty acid levels - PUFA in blood). We will also conduct a follow-up assessment 6 months after the end of the intervention (accelerometer, neurocognitive testing, PUFA levels) to assess PA and MedDiet adherence. We hypothesize that iSTEP (both intervention arms) will increase PA, reduce SB, and improve neurocognition compared to control; the iSTEP + MedDiet group will demonstrate improvement in CVD risk factors and neurocognition compared to the PA intervention alone. Findings from this proposal will lay the groundwork for development of novel large-scale mobile PA/diet interventions dedicated to treating HAND and improving cardiovascular health for PLWH.

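### The text prompts, the listed content of the clearance form and one of two hold rules name only physical activity, so harms of the assigned diet are ascertained less closely, and section 4.2 leaves the hold on the diet unsettled

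*Combined protocol and SAP*

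**What the plan says.** The opening summary gives one arm of 50 daily messages that, besides PA and sedentary behaviour, are to "promote adherence to a MedDiet, including walnut consumption". The protocol recognises diet risk at entry: section 3.1 requires that participants can eat walnuts, and section 3.2 excludes "Tree nut allergy that would prevent walnut consumption or other food restrictions that would prevent participation" in the diet intervention.

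Safety steps after entry are in section 4.2. There are three routes by which events are reported:

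- Participants receive "regular text messages that will solicit information about any adverse events associated with their PA".
- They are "contacted by telephone on a monthly basis by the PI to inquire about any adverse events, including chest pain, dizziness, or falls".
- At enrolment, "participants will be asked to phone the PI if any adverse events occur during study participation".

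For clearance, the primary care physician is contacted "to verify if there are any medical issues that would prevent involvement in this study" and is sent "a medical clearance form that describes the SMS study and lists the options for moderate PA". The physician may allow some activities and not others.

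Section 4.2 states the response to an event twice. Its first paragraph takes the participant out of the study until the physician clears them again in writing. The trigger is an adverse event or a contraindication to moderate PA, with muscle soreness and shortness of breath as examples. Its second paragraph says: "In the case of any adverse events, participant PA activities will be immediately discontinued", with the physician contacted to arrange evaluation and treatment.

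**The concern.** The trial assigns two components, but the specific safety provisions after entry are written for one. If the only regular prompt asks about PA, a participant with a reaction to a food is less likely to be asked about it than a participant with sore muscles. The PA + diet arm is the only one assigned the diet, so its added harms are the ones least directly sought.

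The hold rule raises a second issue. If any adverse event interrupts PA, an event caused by the assigned diet interrupts PA in one arm only. Hypothesis 2.2 compares PA + diet with PA alone and reads the difference as the effect of adding diet. Interruptions of PA confined to one of those arms would blur that comparison.

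**Working it through.** The documents give no safety figure, so there is nothing to recompute. The check is to set the provisions side by side for the two components.

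| Provision | Physical activity | Diet, including walnuts |
|---|---|---|
| Entry criteria (3.1, 3.2) | Readiness questionnaire and exclusions | Nut allergy and food-restriction criteria |
| Physical risks listed (4.1) | Muscle fatigue or soreness | None listed |
| Regular text prompts (4.2) | Asked about | Outside the stated scope |
| Monthly call (4.2) | Any event | Any event, but no diet-specific example among the three named |
| Participant phones in (4.2) | Any event | Any event |
| Question put to physician (4.2) | Study-wide | Study-wide |
| Itemised content of clearance form (4.2) | Options listed, restriction by activity | Not mentioned |
| Hold, first paragraph of 4.2 | Held, as part of the whole study | Held only if the rule covers diet events |
| Hold, second paragraph of 4.2 | Held | Not mentioned |

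**Solicitation.** One of the three routes, the text prompts, is limited to PA. The other two cover any event. A diet-related event can therefore be captured, but by fewer routes than a PA-related one.

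**Clearance.** The question to the physician is general. The form's described content is not: it lists PA options, and the only partial restriction it offers is by activity.

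**Hold.** The trigger in the first paragraph can be read in two ways, because the phrase about moderate PA may qualify only the contraindication or the adverse event as well.

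1. If it covers any adverse event, a diet-related event suspends the participant from the whole study, diet included. The second paragraph then conflicts with it, since it names PA alone.
2. If it covers only PA-related events, a diet-related event falls under the second paragraph alone. PA stops, and nothing says what happens to the diet.

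Under both readings a diet-related event interrupts PA. They differ on whether the diet is also held, and the text does not let staff tell which applies.

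**Scale.** The affected arm is 50 of 150, or 50/150 = one third of the randomised sample. No event rate is given, and section 5 plans no adverse-event analysis, so neither the reporting loss nor the effect on the PA comparison can be calculated.

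**The case against.** The strongest reply is that the general provisions already cover diet. The monthly call asks about any event, and its three examples are introduced as inclusions, not as a complete list. Participants are told to phone about any event, emergencies go to emergency services and then to staff, and text logs are watched daily for serious problems. The physician is asked about anything that would prevent involvement and can refuse participation altogether. The entry criteria remove people with known nut allergy or incompatible food restrictions. Section 5 sets no safety hypothesis to be biased.

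Most of this stands, and it limits the point. A reader might infer that diet-related events would never be asked about. The documents do not support that, because two of the three routes cover any event. A reader might also infer that the rule would stop the wrong component while diet messages carry on. That is not established either: the first paragraph of section 4.2 may suspend the whole study, the second brings in the physician, and no passage says diet messages continue. Nor can it be said that the monthly call leaves diet out, since its script is not given.

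The reply does not explain why the regular prompt is limited to PA when one arm is assigned a second component, and it does not remove the disagreement within section 4.2. Entry exclusions address known allergy and restrictions; they do not provide follow-up of events that arise on study.

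**Conclusion.** The point holds in limited form. The text prompts, the listed content of the clearance form and the hold in the second paragraph of section 4.2 name only PA, although a third of the sample is also assigned a diet with walnuts. Diet-related harms can be captured, but less closely than PA-related ones. The two statements of the hold do not agree, and if the first is limited to PA-related events, neither addresses the diet component.

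This rests on the wording of section 4.2 being what staff follow; the clearance form and call script themselves are not in the documents. The possible effect on hypothesis 2.2 further assumes that some events are caused by the assigned diet and do interrupt PA. The amount of under-reporting, and of any dilution of the PA comparison, is unknown. It is worth correcting because the remedy is cheap and improves the account of harms, not because a bias has been shown.

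**What to change.** - Widen the text prompt and the monthly-call items to cover diet-related as well as PA-related events. Use the same wording and frequency in all three arms, so that background symptoms are counted alike and the arms can be compared.
- Record for each event the component to which it is attributed: PA, diet, other or unclear.
- List the diet component, including walnuts, on the physician clearance form.
- Reconcile the two paragraphs of section 4.2 on what is held after an event, and state how the diet component is handled. The clinical action is for the investigators and the IRB to set; none is proposed here.

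The cost is a few added items in existing texts, calls and the form, plus an IRB amendment. More non-serious events will be recorded.
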